**A Feasibility Study Incorporating DNA Methylation-Predicted Aging with a
Dietary Intervention to Improve Cardiometabolic Health**

1/14/2022

IRB00065273

NCT04361617

A Feasibility Study Incorporating DNA Methylation-Predicted Aging with a Dietary Intervention to Improve Cardiometabolic Health

Principal Investigator:	[name] [contact] [contact]
Co-Investigators:	[name], MPH, RDN [contact]
	[name] [contact]
Funding Source:	Pilot award funded by Wake Forest Clinical and Translational Science Institute (CTSI) and Cardiovascular Sciences Center
Date:	June 5, 2020 February 17, 2021 March 24, 2021 September 1, 2021 November 5, 2021 November 30, 2021 December 21, 2021 January 14, 2022

SCHEMA

We will recruit up to 50 women and men (≥ 35 years) from the surrounding communities with Metabolic Syndrome (Mets). All participants will provide blood samples to determine epigenetic age estimates. Participants who meet eligibility criteria will be asked to participate in a 4-week nuts and extra virgin olive oil (EVOO) intervention. Half of the intervention participants will be randomly selected to be educated about epigenetic age acceleration before the intervention. All participants will have a phone visit after one week of the intervention to assess compliance, and all participants will be contacted by phone after week two of the intervention. Participants will have in person study-related measurements collected at baseline and 4 weeks.

[figure not shown]

Table of Contents

SCHEMA.....
Table of Contents.....
1.0 Introduction and Background.....

1.0 Introduction and Background

Metabolic syndrome (**MetS**) is a collection of at least three out of five cardiometabolic risk factors including abdominal obesity, hypertension, elevated blood glucose, hypertriglyceridemia, and low high-density lipoprotein cholesterol [1]. The prevalence of MetS is rising worldwide, and as of 2012, more than one third of all US adults met the criteria for MetS [2]. This is important as MetS is a major risk factor for cardiovascular disease and is considered a state of prediabetes [3]. Improving metabolic parameters through dietary, behavioral, and pharmacological interventions can improve or reverse MetS [4, 5]. For instance, a 5-year study in Spain (PREDIMED) evaluated the effects of the Mediterranean diet on primary prevention of cardiovascular disease in subjects at high risk of cardiovascular disease (CVD)[6]. PREDIMED was a multicenter, randomized, controlled clinical trial of 7,447 participants who were randomized to one of three diets: Mediterranean diet supplemented with extra virgin olive oil (EVOO), Mediterranean diet supplemented with mixed nuts, or a low-fat control diet. The PREDIMEDstudy found a reduction in the cardiovascular event rates in both intervention groups compared to the low fat control group. Additionally, post-hoc analysis of individuals meeting the criteria for MetS at baseline revealed EVOO and nut consumption (compared to controls) was more likely to result in **reversion of MetS** (HR = 1.35 95% CI: 1.15 – 1.58, $p<0.001$), and significant reductions in central obesity ($p<0.001$) and high fasting glucose ($p = 0.02$) compared to the low fat control group [7]. However, **lower levels of adherence** to the PREDIMED intervention was found in participants with a higher number of cardiovascular risk factors, larger waist circumference, and lower physical activity levels at baseline [8]. New strategies to convey

one's risk of morbidity and mortality at the onset of a dietary intervention may improve intervention adherence, particularly among individuals meeting the criteria for MetS.

DNA methylation patterns change with age, and can be used to estimate chronological age [9-12]. A greater DNA methylation-based predicted age relative to chronological age, often referred to as "**epigenetic age acceleration**", has been associated with many lifestyle factors, including physical activity and diet, as well as components of MetS, including obesity, blood pressure, HDL cholesterol and blood glucose levels [13]. A higher number of MetS components are cross-sectionally associated with epigenetic age acceleration [14]. Epigenetic age acceleration is more strongly predictive for the risk of morbidity and mortality than chronological age [9, 11]. We **hypothesize** that the majority of people with MetS have advanced epigenetic aging, and among those that have advanced epigenetic age, learning about epigenetic age and its relationship to morbidity and mortality at the onset of a dietary intervention will improve participant adherence to the dietary intervention. Further, we hypothesize that daily consumption of EVOO and tree nuts in participants with MetS and advanced epigenetic age could help reverse MetS and potentially slow epigenetic aging. Therefore, we plan to conduct this feasibility pilot study to:

1.1 Primary Objectives

To determine the proportion of participants with MetS with epigenetic age acceleration

To assess adherence to daily EVOO and tree nut consumption over the 4-week intervention, and compare adherence in participants educated about epigenetic age acceleration at baseline compared to intervention arm not educated about epigenetic age acceleration

Qualitatively explore how participants perceive epigenetic age, and how participants' experiences would impact the feasibility of a larger clinical intervention in terms of challenges and motivators

1.2 Secondary Objectives

Compare epigenetic age acceleration before and after the 4-week intervention

1.3 Exploratory Objectives

Compare changes in MetS related traits (body mass index, waist circumference, blood pressure, HDL cholesterol, triglycerides, HbA1c, and fasting glucose levels) before vs. after the 4-week intervention

2.0 Participant Selection

This study can fulfill its objective only if participants appropriate for this intervention are enrolled. All relevant medical and other considerations will be taken into account when deciding whether this protocol is appropriate for a particular candidate.

2.1 Inclusion Criteria

- 2.1.1 Men and Women \geq 35 years of age
- 2.1.2 Metabolic syndrome, defined as \geq 3 of the following:

- 2.1.2.1 Waist circumference >102 cm in men and >88cm in women
- 2.1.2.2 Triglycerides >150 mg/dL AND/OR drug treatment for elevated triglycerides
- 2.1.2.3 HDL cholesterol <40 mg/dL in men and <50 mg/dL in women AND/OR drug treatment for reduced HDL cholesterol
- 2.1.2.4 Systolic blood pressure >130 mm Hg or diastolic blood pressure >85 mmHg AND/OR antihypertensive drug treatment
- 2.1.2.5 Fasting glucose >100 mg/dL or hemoglobin A1c > 5.6% AND/OR oral hypoglycemic medications
- 2.1.3 Willing to comply with study visits, as outlined in the protocol
- 2.1.4 Able to read and speak English
- 2.1.5 No allergies or hypersensitivities to olive oil or nuts
- 2.1.6 Ability to understand and the willingness to sign a written informed consent document.
- 2.1.7 Completion of a validated 14-item Mediterranean Diet Assessment Screener to assess baseline dietary consumption of nuts and olive oil

2.2 Exclusion Criteria

- 2.2.1 Plans to move from the study area in the next 12 weeks
- 2.2.2 Body Mass Index (BMI) $\geq 40 \text{ kg/m}^2$
- 2.2.3 Dementia that is medically documented or suspected, or clinical evidence of cognitive impairment sufficient to impair protocol adherence
- 2.2.4 Candidate with any dietary practice, behavior or attitude that would substantially limit ability to adhere to protocol
- 2.2.5 Homebound for medical reasons
- 2.2.6 Living in the same household with another participant
- 2.2.7 Insulin-dependent Diabetes

2.3 Inclusion of Women, Minorities and Children

Males and females of all races and ethnic groups are eligible for this trial. Children will not be included in this study as children with metabolic syndrome may have very different underlying etiologies for metabolic syndrome than adults.

2.4 Identification of Cohort

We propose to draw our sample of 50 men and women from the population residing in Winston-Salem/Forsyth County, North Carolina. Over 361,220 persons live in the county. In addition, over 1.3 million people reside in the eight contiguous counties comprising the Piedmont Triad area. We anticipate that recruitment for the study can be accomplished in Forsyth County. However, if needed, we will extend recruitment to the surrounding communities.

3.0 Recruitment Procedures

Investigators at Wake Forest School of Medicine have extensive experience in recruitment for both observational and clinical trials. Based on our previous experience in large-scale studies, we have found the use of several approaches for recruitment substantially better than relying on one recruitment strategy. These approaches include: community-wide methods designed to reach large numbers of men and women and contacting participants through MyWakeHealth communications. We will also recruit participants through advertising on the WFBH website

‘Be Involved’ and using study flyers posted at local medical clinics including Family Medicine and Internal Medicine.

We anticipate it will take approximately 12 weeks to recruit 50 participants for this project. Candidates will complete a telephone screening. The baseline visit will consist of an in-person assessment visit, scheduled for a morning time, and participants will be asked to be fasting and will be instructed to bring their medications to the visit. Candidates will review the informed consent document at the baseline visit for in-person screening with study staff prior to beginning their participation.

Each candidate will be greeted by a study staff member who will take the candidate to a private consulting room. A final eligibility checklist and each section of the informed consent will be reviewed with the candidate. Once the candidate fully understands each section of the consent, he/she will sign the document and be given a copy to take home. A copy will be retained by the study staff.

Recruitment of Participants

The goal of the recruitment phase is to enroll 50 men and women with MetS into the study.

	Female	Male
American Indian or Alaska Native	1	1
Asian or Pacific Islander	1	1
Black, not of Hispanic Origin	6	6
Hispanic	2	2
White, not of Hispanic Origin	14	14
Other or Unknown	1	0
TOTAL	25	25

3.1 Epigenetic Age Acceleration

For all participants providing informed consent, blood samples will be collected at each in-person visit to calculate epigenetic age acceleration.

4.0 Treatment Plan: Tree Nuts and Extra Virgin Olive Oil

At the intervention visit, all participants will receive the full 4-week supply of EVOO and tree nuts, including unsalted English walnuts, almonds or pistachios (approximately 10-day supply of each type). Participants will be asked to supplement their normal diets with these products and will be provided recipes and other information that will allow them to replace other foods with the nuts and oil. We will ask participants to consume one ounce of tree nuts per day and two tablespoons of EVOO per day by incorporating these foods into their diet. Dietary adherence diaries will be given to measure incorporation of the study foods.

Participants will be randomized to learn about epigenetic age acceleration (arm 1) or not to learn about epigenetic age acceleration (arm 2) in a 1:1 allocation at the intervention visit. Those in the intervention arm 1 that are to learn about epigenetic age acceleration will receive some educational materials and a brief description of epigenetic age acceleration.

A telephone visit will be conducted at the end of week 1 for additional diet counseling, to assess safety/potential side effects, to collect adherence diaries. A follow-up phone call for compliance assessment and to answer participant questions will be conducted at the end of week 2. A final measurement visit will be scheduled for the end of week 4 for a morning time and participants will be asked to be fasting.

4.1 Toxities

Side effects will be monitored by staff contact at the end of week 1 visit, and at the end of week 2 (by phone) and at the final measurement visit at the end of week 4. Participants will be encouraged to contact the Study manager during the study period if they feel they are experiencing effects related to the study foods.

EVOO and tree nuts are generally recognized as safe and are consumed by free living adults on a regular basis. The amount to be given in this study are within the range given to the participants in the PREDIMED study [6] and found to have only minor side effects, mainly stomach upset, bloating and nausea, and none of the side effects advanced to serious adverse events.

Administration

Study foods will consist of one ounce of tree nuts per day and two tablespoons of EVOO per day. Participants will be instructed how to consume the proper amount of tree nuts and EVOO and reporting the consumption on the compliance diary (Appendix A). The tree nuts will be provided in daily servings (one ounce per day) and EVOO will be provided in bottles, along with a tablespoon. Participants will be instructed to use the tablespoon to measure EVOO. Participants will also receive recipes and other written information that will assist them in incorporating both the nuts and EVOO into their existing dietary patterns.

Dose Modification/Toxicity management:

Side effects will be monitored via the telephone visit at the end of week 1 and 2 and by participant report. Participants will be encouraged to contact the study team during the study period if they feel they are experiencing side effects related to the study foods. For those participants with existing medical conditions (e.g., gallbladder removal or bariatric surgery) or who are experiencing nausea related to consumption of the olive oil, a titrated dosing plan will be used. These participants will begin their olive oil consumption at 1 tablespoon/day for 5 days and increasing to 2 tablespoons/day on the sixth day if it is well tolerated. If this increase is not tolerated, the participant can be returned to 1 tablespoon per day and attempt an increase after an additional 5 days.

Withdrawal from study intervention

Any side effects experienced by the participant may or may not be due to the study foods. If the side effects become intolerant for the participant, he/she may be withdrawn from the study at the discretion of the study team.

4.2 Table of Study-Related Interventions

Measure	Baseline: In-person screening visit	Intervention visit	End of Week 1 Phone Call	End of week 2 Phone Call	Final in person visit
Anthropometrics					
Body weight	X				X
Height	X				X
Waist circumference	X				X
Blood collection	X	X			X
Blood pressure	X				X
Demographics	X				
Mediterranean diet screener	X				X
Health History/health habits	X				X
Adherence/safety assessment			X	X	X
Intervention Experience Assessment and Perception of Epigenetic Age Assessment (arm 1 only)					X
Dispense study foods		X			

4.3 Study Visits

4.3.1 Baseline Visit: In-person screening

At the in-person screening visit each participant will be greeted by a staff member who will take the candidate to a private consulting room. A final eligibility checklist and each section of the informed consent will be reviewed with the candidate. Once the candidate fully understands each section of the consent, he/she will sign the document and be given a copy to take home. A copy will be retained by the study staff.

After providing informed consent, fasting participants will complete study questionnaires in a quiet private room and show current medications to a staff member that will record the names of medications brought to the clinic. Next, blood pressure will be measured after resting 5 minutes and sitting upright. Blood pressure may be measured twice. Body weight will then be measured using a beam scale with movable weights with participant wearing indoor clothing with no shoes. Height and waist circumference will also be measured. Participant will also have a fasting blood collection. Participants will be asked to complete a validated 14-item Questionnaire of Mediterranean diet adherence [15] to assess their baseline diet including consumption of olive oil and nuts (Appendix B).

4.3.2 Intervention visit

Eligible participants (those that provided informed consent, were fasting at the in-person visit and met the criteria for MetS, and provided blood samples for epigenetic age acceleration

measurements) will be contacted to schedule the intervention visit. The study is set to end on March 21, 2022, which means the study intervention visits need to be completed by March 3, 2022. Participants that have not attended their intervention visit by March 3, 2022 will be discontinued from the study.

At the intervention visit, participants will have a fasting blood collection. Participants will receive counseling and recipes to help them incorporate the nuts and EVOO into daily meals. Dietary adherence diaries will be given to participants to measure incorporation of the study foods and participants will be instructed to complete the adherence diaries on a daily basis. Participants will be given a 4-week supply of EVOO, tree nuts, and a tablespoon for measuring the EVOO.

Participants will be randomized to learn about epigenetic age acceleration (arm 1) or to not learn about epigenetic age acceleration (arm 2) in a 1:1 allocation at the baseline visit. Those in arm 1 will receive some educational materials and a brief explanation of epigenetic age acceleration. At the end of this visit, all participants will be scheduled for the remainder of their telephone and in person study visits.

4.3.3 End of week 1 and week 2 telephone calls

During the end of week 1 telephone call, participants will be contacted via telephone and asked questions about their adherence, and any potential side effects observed. Participants will receive additional counseling for how to incorporate the nuts and oil into a daily meal as needed. A follow up phone call at the end of week 2 will be scheduled to assess compliance and to answer participant questions, and a final measurement visit will be scheduled for the end of week 4 for a morning time and participants will be asked to be fasting.

4.3.4 Final measurement visit, end of week 4

The same measures, as listed in the in-person screening visit will be performed. Study questionnaires, with the exception of demographics and health history, will be distributed and completed, and adherence diaries will be collected.

For participants of the intervention arm 1 (participants educated about epigenetic age acceleration), a self-administered exit questionnaire will be given to qualitatively explore participants' perception of epigenetic age, and challenges and motivators for behavior change during the intervention. The open-ended questions will be designed to ascertain understanding of epigenetic age, and assess the challenges and motivators participants encountered during the intervention.

Participants in both arms will be administered an Intervention Experience Assessment to explore how participants' experiences would impact the feasibility of a larger clinical intervention in terms of challenges and motivators.

5.0 Study Measures

5.1 Anthropometric Measures

Weight: Weight will be assessed using a digital scale in kilograms with participants wearing indoor clothing with no shoes.

Height: Height will be measured using a stadiometer attached to a beam scale, in centimeters, with no shoes worn.

Blood pressure: First-phase systolic and fifth-phase diastolic Korotkoff blood pressure will be auscultated from the right arm of the subject, after resting 5 minutes and sitting upright. We will use a standard manometer with a cuff sized appropriately. . If the blood pressure reading is elevated, it will trigger an "alert" and subsequent participant/physician notification.

Waist circumference: Waist circumference will be measured at the midpoint between the lowest rib and the iliac crest.

5.2 Blood-based Biomarkers

HDL cholesterol, triglycerides, HbA1c, and fasting glucose levels will be analyzed using serum samples at a local LabCorp facility.

Epigenetic age acceleration: DNA methylation will be measured from blood samples frozen/ stored at -80 C within 2 hours of collection. After recruitment of 50 participants meeting the criteria for MetS is completed, blood samples will be sent for DNA methylation analysis in the lab of [name] at WFBMC. DNA will be extracted from whole blood samples, and will be bisulfite-converted using the EZ DNA Methylation Gold kit (Zymo, Irvine, CA). Illumina Infinium MethylationEPIC BeadChip, which targets over 850,000 CpG sites, and the Illumina iScan Reader will be used to determine the proportion of DNA methylation at each site. The ratio of the fluorescence intensity of the methylated versus the combined methylated and unmethylated probes will be determined with Illumina GenomeStudio. As a quality control measure, the cumulative fluorescent signal must be significantly greater than the negative controls included for each sample. We will use a threshold of this "detection p-value" of ≤ 0.05 in at least 90% of the samples as criteria for adequate assays. Finally, adjustments will be made to normalize the fluorescent signals from the Infinium I and Infinium II fluorescent assays used prior to analysis (in Bioconductor).

DNA methylation profiles (beta-value, after adjustment chip and position effects) at 1,030 unique DNA methylation profiles will be used for epigenetic age acceleration predictions, using the DNA GrimAge predictor [11]. We will calculate predicted lifespan and regress predicted lifespan on chronological age to produce estimates of epigenetic age acceleration.

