8.1 Prevalence of epigenetic age acceleration

Primary Outcome 1: proportion of participants with MetS with advanced epigenetic aging

To characterize the relationship between MetS and epigenetic aging, we will examine epigenetic age acceleration prevalence among the 50 participants with metabolic syndrome. Epigenetic age acceleration will be calculated as described in 5.2. Advanced epigenetic age acceleration will be defined as a positive epigenetic age acceleration (higher than expected based on chronological age).

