8.4 Test for changes in epigenetic age acceleration

Secondary outcome: Changes in epigenetic age acceleration

It is not clear if changes in nut and EVOO consumption can slow or reverse epigenetic age acceleration. As a secondary goal, we will compare change in epigenetic age acceleration from the baseline visit to the intervention visit (control period) to change in epigenetic age acceleration from the intervention visit to the final visit using a paired sample t-test.

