Appendix D.

We would like to ask you some questions about epigenetic age. Epigenetic age is a DNA-based measure that predicts the biological age of your cells. Having an accelerated epigenetic age means that the biological age of your cells may be more advanced than your chronological age.

20. Using the scale below, indicate how much you want to know your epigenetic age:

[figure not shown]
1 Not at all	2 Not much	3 Neutral	4 Somewhat	5 Very much
-----------------	---------------	--------------	---------------	----------------

21. For question #1, why did you select that answer?

[figure not shown]
22. Before beginning this study, if you were told your epigenetic age appeared more advanced than your chronological age, do you think you would be more or less motivated to eat the nuts and olive oil everyday?

1 Not motivated at all	2 Less motivated	3 Neutral	4 More motivated	5 Very motivated
---------------------------	---------------------	--------------	---------------------	---------------------

[figure not shown]
23. Before beginning this study, if you were told your epigenetic age appeared younger than your chronological age, do you think you would be more or less motivated to eat the nuts and olive oil everyday?

24. If eating tree nuts and olive oil slowed biological aging, how likely would you be to continue to eat tree nuts and olive oil daily?

25. If consuming olive oil slowed biological aging, how likely would you be to continue to consume olive oil daily?

26. Do you feel we did a good job explaining the concept of epigenetic aging?

27. For question #76, can you comment on why you selected that answer?

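### Section 5.2 regresses predicted lifespan where the rest of the plan means predicted age; followed literally, this reverses the 8.1 labels and the direction of the 8.4 change

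*Combined protocol and SAP*

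**What the plan says.** The concept appears in Section 1.0, where acceleration is "A greater DNA methylation-based predicted age relative to chronological age". Appendix D gives participants the same meaning: "Having an accelerated epigenetic age means that the biological age of your cells may be more advanced than your chronological age". Section 8.6 frames its power statement on the difference between epigenetic and chronological age. In all three, a higher value is worse.

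The calculation appears only in Section 5.2: "We will calculate predicted lifespan and regress predicted lifespan on chronological age to produce estimates of epigenetic age acceleration". Lifespan is named twice in that sentence.

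Section 8.1 joins the two. It says "Epigenetic age acceleration will be calculated as described in 5.2", and then sets the rule for Primary Outcome 1: "Advanced epigenetic age acceleration will be defined as a positive epigenetic age acceleration (higher than expected based on chronological age". Section 8.4 uses the same quantity for the secondary outcome. It compares the change over the control period (baseline to intervention visit) with the "change in epigenetic age acceleration from the intervention visit to the final visit using a paired sample t-test".

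No section states the scale or direction of the predictor's output, and none reverses a sign between 5.2 and 8.1.

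**The concern.** A lifespan longer than expected for one's age is favourable; a predicted age higher than expected is unfavourable. A positive residual therefore means opposite things depending on which quantity is regressed. Section 8.1 takes the 5.2 residual unchanged and attaches the unfavourable label to positive values. An analyst who follows 5.2 to the letter would label as advanced the participants with the longer predicted lives, and would report a benefit of the study foods in 8.4 as a worsening.

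Section 5.2 is the sole operational definition behind Primary Outcome 1 and the secondary outcome. Section 8.6 says the study exists to supply prevalence and effect-size estimates for a larger trial, and an effect size of uncertain sign is a poor input for that.

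**Working it through.** **The plan's own figure first.** Section 8.6 gives 0.80 power for 0.4 SD with 50 people at α = 0.05. As a one-sample or paired test, two-sided (an assumption, since sidedness is not stated):

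- Normal approximation: 0.4 × √50 = 2.828; 2.828 − 1.960 = 0.868; power = Φ(0.868) = 0.807.
- Noncentral t with 49 degrees of freedom: power = 0.792.
- Required n = ((1.960 + 0.842)/0.4)² ≈ 49.1, rounded up to 50.

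The figure is reproduced. Power depends only on the absolute effect size, so it is the same whichever way the outcome points.

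**Sign of the residual.** Let A be predicted age and L predicted lifespan, and suppose L = c − kA with k > 0. Regression residuals are linear in the outcome, so

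residual(L on age) = −k × residual(A on age).

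Every positive residual becomes negative and the reverse (ignoring ties), so P(residual L > 0) = 1 − P(residual A > 0). It makes no difference whether L is remaining or total lifespan, because adding age to the outcome leaves its residual on age unchanged.

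**How many labels flip.** Simulation: n = 50, 5,000 replicates, age uniform from 35 to 75, acceleration SD 4 years, least-squares residuals from the same sample. All of these except n are assumptions.

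| Lifespan as a mirror of predicted age | Correlation of the two residuals | 8.1 labels flipped |
|---|---|---|
| Exact | −1.00 | 100% |
| Added noise, SD 2 years | −0.89 | about 85% |
| Added noise, SD 4 years | −0.70 | about 75% |
| Output is age-scaled after all | not applicable | none |

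**Effect on the reported proportion.** In-sample residuals average zero. In the same simulation the share above zero averaged 0.50 (95% range 0.42 to 0.58) in the age orientation, and it also averaged 0.50 in the lifespan orientation. This held when the true share with epigenetic age above chronological age was set to about 50%, 69% or 89%. Under an exact mirror the two in-sample shares do sum to 1, but both sit close to one half. A material swap, such as 70% reported as 30% (1 − 0.70 = 0.30), needs expected values from an external reference, and the plan describes none.

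**Effect on 8.4.** A true slowing of d becomes a reported rise of kd, which equals d only if k = 1. In one simulated data set of 50 pairs, negating the outcome moved t from −3.26 to +3.26, with two-sided p = 0.0020 both times. Direction reverses; significance does not. This takes the residuals from one regression common to all visits. If the regression were refitted at each visit on the same people, residuals would average zero at every visit and the mean change would be zero in either orientation; the plan does not say which is intended.

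**The case against.** The strongest reply is that the intended direction is not in doubt. Section 1.0, the parenthesis in 8.1, Section 8.6 and Appendix D all point the same way. In 5.2 itself, the preceding sentence says the methylation profiles "will be used for epigenetic age acceleration predictions, using the DNA GrimAge predictor [11". A competent analyst might take predicted lifespan as loose wording for an age-scaled output, and then no label or sign reverses.

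Much of this stands. A reader might infer that the wrong participants will certainly be labelled. The documents do not support that, because they never give the output's scale or direction. They do not rule it out either: the reference list gives the predictor paper a title about predicting lifespan, so the literal reading is plausible. The other statements show what was meant; 5.2 is the instruction that 8.1 tells the analyst to carry out.

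A reader might also infer that Primary Outcome 1 would be reported as the complement of the true prevalence. That does not follow from the plan as written, since in-sample residuals give about 50% under both readings. Nor is the 8.4 test invalid or the 8.6 power wrong; neither depends on sign. The unchanged p-value is limited comfort, though, because 8.4 asks whether the foods slow or reverse acceleration, and direction is the answer to that question.

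**Conclusion.** The point holds conditionally. The rule in 5.2, carried into 8.1, contradicts the plan's own concept of acceleration and is wrong as written. Taken literally, it reverses individual labels in 8.1 (all under an exact linear mirror, roughly 75% to 85% under the noise levels assumed here) and reverses the direction of the 8.4 estimate. Taken as loose wording, it reverses nothing, and only the sponsor can say which was meant. The reported proportion, the two-sided p-value in 8.4 and the power in 8.6 are essentially untouched under either reading, unless an external reference is used for the proportion.

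The conclusion rests on lifespan falling as predicted age rises. The noisy-mirror percentages rest on the simulation assumptions listed above.

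The absence of a stated reference for the regression is a separate matter. It is what holds the proportion near 50%, and correcting the sign does not cure it.

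**What to change.** In 5.2, replace the regressed quantity. Suggested text: *We will calculate the GrimAge epigenetic age estimate and regress it on chronological age; the residual (observed minus expected) is epigenetic age acceleration, with positive values meaning older than expected.* The sponsor should confirm the scale and direction of the predictor's output when adopting this wording, because the documents do not give them.

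In 8.4, add that a negative change in acceleration means slowing, so that benefit relative to the control period is a lower change over the intervention period than over the control period.

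The rule in 8.1 then needs no change of wording on this point. The cost is a sentence or two in each of 5.2 and 8.4, with no new data, assay or sample size.
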